2.5 Post-operative evaluation

All patients were actively clinical followed up regularly at 3, 6, 12 and 24, included GERD-HRQL. UE was performed in all patients at 12 or 24 months. Significant vomiting and food intolerance were evaluated at 6, 12 and 24 months follow-up. Vomiting was considered significant when occurring at least three times a week and food intolerance was defined as vomiting occurring almost each day. Esophageal biopsies were performed only in case of esophagitis \geq B (9).

Weight loss parameters were recorded at 3, 6, 12 and 24 months after the LSG : BMI (in kg/m²), %EWL and percentage total weight loss %TWL from baseline. The secondary endpoints were GERD and esophagitis studied with Upper endoscopy and GERD score

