Study Protocol

“Does Antrum Size Matter in Sleeve Gastrectomy?”

Study Protocol

“Does Antrum Size Matter in Sleeve Gastrectomy? ”

BACKGROUND

Laparoscopic sleeve gastrectomy (LSG) is currently the most frequent primary bariatric procedure performed worldwide. LSG is safe and effective in terms of excess weight loss. It is a powerful metabolic operation that activates significant hormonal pathways that lead to changes in eating behavior, glycemic control and intestinal functions. LSG can be a faster procedure for its technical aspects (any need for intestinal anastomosis, being limited to the stomach transection). The most frequent and sometimes dangerous complications are leaking, hemorrhage, splenic injury, stenosis and Gastroesophageal Reflux Disease (GERD)(1). Despite its established efficacy and safety, dispute still exists on optimal operative technique for LSG: bougie size, distance of resection margin from the pylorus, the shape of section at the gastroesophageal junction, staple line reinforcement and intraoperative leak testing are among the most controversial issues (2). Indeed, different Authors have adopted a resection distance from the pylorus between 2 and 6–7 cm with various reasons (3). In favor of resections more distant to the pylorus, Authors argue that it seems to improve gastric emptying, prevent distal stenosis and reduce intraluminal pressure, potentially leading to a lower incidence of fistula and/or reflux. On the other hand, resections close to the pylorus seems to reduce more the gastric distensibility and increase intragastric pressure, potentially leading to a better satiation with less oral intake (4, 5). However, only few studies have investigated the differences between these two approaches (3). Thus, the primary aim of this randomized monocentric study is to evaluate variations in percentage of excess weight loss (%EWL) at 1 and 2 years follow-up after LSG in subject with a gastric resection starting from 2 cm from the pylorus (wide antrectomy) compared to those with a gastric resection starting from 6 cm from the pylorus (small antrectomy). Secondary aim-points are represented by evaluation of differences in morbidity, mortality, tolerance to food, incidence of reflux symptoms and GERD Health-Related Quality-of-Life (GERD-HRQL) score between the two groups.

Material and Methods

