2.2 Study Design

The study is designed as a randomized controlled trial. Primary outcome was the evaluation of %EWL between 2 groups. Secondary outcomes were evaluation of morbidity, mortality, incidence of reflux symptoms and Quality of Life score between the Groups.From January 2015 to November 2017, a series of 218 consecutive patients suffering from morbid obesity and scheduled for LSG were included; informed consent was obtained from each participant before surgery.

Inclusion criteria were morbid obesity defined as BMI 40 kg/m² and age between 25–50 years old. Obesity-related comorbidities included Type 2 Mellitus Diabetes (T2MD), hypertension, hyperlipidemia, bronchial asthma, osteoarthritis and degenerative joint disease.

Exclusion criteria

Patients with previous bariatric surgical procedures, endocrine disorders causing obesity (as hypothyroidism and Cushing disease), pregnancy or lactation, psychiatric illness, or recent diagnosis of malignancy, inflammatory bowel disease, Barrett's esophagus, and GERD with esophagitis scored as or greater than grade B, a large hiatal hernia (>3 cm) were excluded from the study. In case of absence or grade A esophagitis, GERD was also considered as severe with GERD-HRQL > 30 and when interfering with daily activities or inducing dietary restriction despite, also these were excluded.

One hundred-fifty patients were considered eligible and randomized in two Group (Group A n = 75, Group B n=75). All patients underwent elective laparoscopic LSG. In the case of conversion to open surgery, patients were excluded. Details of enrollment procedure are shown in Fig. 1.

Randomization

Participants were randomly assigned to one of the two groups using computer-generated permuted blocks (www.randomization.com). Outpatient clinic controls were done by surgeons/surgical residents/GP blinded for the groups. Patients were randomized into 2 groups based on the distance to pylorus of resection: Group A (n=75) at 2 cm, Group B(n=75) at 6 cm. Results were obtained at 1 and 2 years follow-up. The randomization scheme was generated using the web site Randomization.com (<http://www.randomization.com>).

Blinding Process

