2.6 Statistical Analysis

Statistical analysis was performed using Graphpad Quick Calcs (GraphPad version 6.04 for Windows, GraphPad Software, La Jolla California USA). Baseline comparisons were performed using chi-square tests and T-tests. Continuous variables are expressed as mean \pm standard deviation (SD). Differences between preoperative and postoperative parameters were compared by Wilcoxon paired rank test. For all tests, a two-sided $p < 0.05$ was considered statistically significant.

Sample size

THIS IS A CONTROLLED RANDOMIZED STUDY OF BINARY NON-INFERIORITY OUTCOME IN PARALLEL GROUPS. IF THERE IS TRULY NO DIFFERENCE BETWEEN THE STANDARD AND EXPERIMENTAL TREATMENT, THEN 138 PATIENTS ARE REQUIRED TO BE 90% SURE THAT THE LOWER LIMIT OF A ONE-SIDED 95% CONFIDENCE INTERVAL (OR EQUIVALENTLY A 90% TWO-SIDED CONFIDENCE INTERVAL) WILL BE ABOVE THE NON-INFERIORITY LIMIT OF -10. SAMPLE SIZE WAS CALCULATED WITH SEALED ENVELOPE LTD. 2012.

Appendix 2

Chief Investigator: [name], PhD – UOC Chirurgia Generale – Ospedale A. Rizzoli –

Lacco ameno napoli. [contact]; cellulare: [name].

Results summarized in the table:

Table 1 :Preoperative demographics data

Table 2: Weight, Body mass index, and the percentage of excess body weight loss and the Percentage Total Weight loss of the two groups at follow-up 3-6-12-24-months

Table 3: GERD Health-Related Quality-of-Life (GERD-HRQL) Score preoperative and postoperative scores follow-up 3-6-12-24 months

Table 4: Endoscopy Preoperative and at 1 and 2 years follow-up into two Groups

Table 1 Preoperative demographics data

Patients	Total	Group A (n=75)	Group B(n=75)
Age	33.6 ± 14	32.2 ± 8	34.2 ± 9
Male	39%	35%	38%
Female	61%	63%	62%
Height	151.2 ± 22	150.1 ± 23	152.8 ± 33
Weight kg	121.9 ± 21.7	124.5 ± 26.7	125.3 ± 23.5
BMI	44.23 ± 6.32	43 ± 8 (40–57)	44 ± 4(40–55)
ASA(I-II)(%)	65%	64%	66%
ASA(III-IV)(%)	35%	36%	34%
T2MD(%)	12(8.%)	7(9.3%)	5(6.6%)
Chronic obstructive pulmonary disease(%)	7(4.6%)	2(2.6%)	3(4%)
Heart Ischemia	1	0	0
Hypertension(%)	95(63%)	55(73.3%)	40(53.4%)

BMI body mass index, %EWL percentage excess weight loss, %TWL percentage total weight loss, Type 2 Mellitus Diabetes (T2MD)

Table 2: Weight, Body mass index, and the percentage of excess body weight loss and the Percentage Total Weight loss of the two groups at follow-up

Patients	3 months follow-up		p	6 months follow-up		p	12 months follow-up		p	24 months follow-up		p
	145/150			141/150			136/150			131/150		

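### Table 3 reports vomiting and food intolerance at 3 months, which section 2.5 does not list for them; 3-month vomiting is the only one of these comparisons whose counts give p<0.05, although P<0.05 is also printed where the counts do not support it.

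*Combined protocol and SAP*

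**What the plan says.** Section 2.5 gives one schedule for clinic visits and the reflux score: "All patients were actively clinical followed up regularly at 3, 6, 12 and 24, included GERD-HRQL". It gives the same four times for weight. For the two outcomes at issue it gives a shorter list: "Significant vomiting and food intolerance were evaluated at 6, 12 and 24 months follow-up". The definitions follow: "Vomiting was considered significant when occurring at least three times a week and food intolerance was defined as vomiting occurring almost each day".

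The Background names food tolerance among the secondary aims: "differences in morbidity, mortality, tolerance to food, incidence of reflux symptoms". Section 2.2 leaves it out: "Secondary outcomes were evaluation of morbidity, mortality, incidence of reflux symptoms and Quality of Life score between the Groups". The closing sentence of section 2.5 names only GERD and esophagitis as secondary endpoints.

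Section 2.6 sets the threshold: "a two-sided $p < 0.05$ was considered statistically significant". Its only named tests for comparing the arms are for baseline: "Baseline comparisons were performed using chi-square tests and T-tests". It names no test for post-operative proportions and no rule for repeated visits.

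Table 3 has a row for significant vomiting and a row for intolerance to food, each at 3, 6, 12 and 24 months. The vomiting row carries P<0.05 at all four times. The intolerance row carries P<0.05 at 3 months and p>0.05 afterwards.

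**The concern.** Three things bear on how Table 3 can be read.

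- **Timing.** The sentence on vomiting and intolerance omits 3 months, while the visit and weight schedules in the same section include it. Table 3 reports 3 months for both outcomes without comment.
- **Printed significance.** A reader of the table would conclude that the 2 cm resection causes significantly more vomiting at every visit up to two years. If the counts support this only at 3 months, the whole claim rests on the one time that section 2.5 does not list.
- **Content of the endpoint.** Food intolerance means only near-daily vomiting. A patient who cannot manage ordinary food but does not vomit almost daily counts as tolerant. The 0 v 0 entries at 12 and 24 months could then be taken as equal food tolerance, which they cannot show.

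**Working it through.** **Inputs.** Counts and denominators are from Table 3, Group A v Group B. The criterion is two-sided 0.05 from section 2.6. Since no test is named for these proportions, two were used: Fisher's exact test, preferred because events are few, and Pearson chi-square without correction.

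For a 2×2 table with events a and c, non-events b and d, and total N:

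χ² = N(ad − bc)² / [(a+b)(c+d)(a+c)(b+d)]

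**Vomiting, 3 months** (11/72 v 3/73): a=11, b=61, c=3, d=70. ad − bc = 770 − 183 = 587. χ² = 145 × 587² / (72 × 73 × 14 × 131) = 49,962,505 / 9,639,504 = 5.18, p=0.023.

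**Vomiting, 6 months** (6/70 v 2/71): ad − bc = 414 − 128 = 286. χ² = 141 × 286² / (70 × 71 × 8 × 133) = 2.18, p=0.140.

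**Vomiting, 12 months** (6/67 v 2/69): ad − bc = 402 − 122 = 280. χ² = 136 × 280² / (67 × 69 × 8 × 128) = 2.25, p=0.133.

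**Vomiting, 24 months** (2/65 v 1/66): ad − bc = 130 − 63 = 67. χ² = 131 × 67² / (65 × 66 × 3 × 128) = 0.36, p=0.550.

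**Intolerance, 3 months** (2/72 v 0/73): ad − bc = 146. χ² = 145 × 146² / (72 × 73 × 2 × 143) = 2.06, p=0.152.

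**Intolerance, 6 months** (1/70 v 0/71): ad − bc = 71. χ² = 141 × 71² / (70 × 71 × 1 × 140) = 1.02, p=0.312.

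| Outcome | Month | A | B | Printed | Chi-square p | Fisher p | Supported? |
|---|---|---|---|---|---|---|---|
| Vomiting | 3 | 15.3% | 4.1% | P<0.05 | 0.023 | 0.026 | yes |
| Vomiting | 6 | 8.6% | 2.8% | P<0.05 | 0.140 | 0.166 | no |
| Vomiting | 12 | 9.0% | 2.9% | P<0.05 | 0.133 | 0.162 | no |
| Vomiting | 24 | 3.1% | 1.5% | P<0.05 | 0.550 | 0.619 | no |
| Intolerance | 3 | 2.8% | 0 | P<0.05 | 0.152 | 0.245 | no |
| Intolerance | 6 | 1.4% | 0 | p>0.05 | 0.312 | 0.497 | yes |

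Intolerance at 12 and 24 months is 0 v 0, so there is nothing to test.

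**Does the choice of test matter?** Yates-corrected chi-square, likelihood-ratio, Barnard, Boschloo and unpooled Wald tests were also run. At 3 months, two-sided vomiting p-values run from 0.019 to 0.046. At 6, 12 and 24 months, the lowest vomiting p under any variant, one-sided tests included, is 0.067. The lowest two-sided p for 3-month intolerance is 0.093. No test tried yields the four unsupported entries.

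**Repeated visits.** Bonferroni over four vomiting comparisons gives 0.05/4 = 0.0125. The 3-month row as printed does not meet it under any two-sided test tried.

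**Nesting of the two rows.** By definition, near-daily vomiting is also vomiting at least three times a week, so intolerant patients should already be in the vomiting row. No section says how the rows were counted. If they are instead mutually exclusive, all significant vomiting is 11 + 2 = 13/72 v 3/73 at 3 months (Fisher p=0.008) and 6 + 1 = 7/70 v 2/71 at 6 months (p=0.097), and the later visits do not change. The listed visits still show nothing below 0.05.

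**A caution on the source.** Table 3's column headings carry p entries of their own, p>0.05 at 3 and 24 months, which disagree with some row entries. This may come from the page layout, so the row entries were used.

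**The case against.** The case on the other side has four parts.

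*The 3-month result may be perfectly regular.* Section 2.5 is in the past tense, and the document already contains results. All patients had a 3-month clinic visit, and the list of tables gives Table 3 as covering 3, 6, 12 and 24 months, although its title there names only GERD-HRQL. A 3 may simply have dropped out of one sentence. This stands. A reader might infer that the 3-month comparison was added after the data were seen, but the documents do not show that. They show two statements that disagree.

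*As printed, the vomiting claim does not rest on 3 months alone.* Table 3 flags every visit. This is true of the printed table, and it is why relabelling 3 months would not be enough: it would demote the one supported entry and leave three unsupported ones to be cited.

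*Food tolerance was measured.* A reader might infer that this aim was not measured at all, or must be withdrawn. Neither follows. There is an operational definition and a reported row. The defensible criticism is that the measure is narrow and that no other instrument is described. Replacing the two rows with one ordered endpoint would be a matter of preference.

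*Overlap of the two rows is not proven.* This also stands. The GERD-HRQL bands in the same table are mutually exclusive and sum exactly to the denominators at 3, 6 and 12 months (at 3 months 38+29+5=72 and 57+15+1=73). The vomiting rows might follow that convention, despite their definitions.

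**Conclusion.** The point holds as a reporting and consistency fault in secondary outcomes. Section 2.5 and Table 3 disagree on whether vomiting and food intolerance were assessed at 3 months. Four printed P<0.05 entries (vomiting at 6, 12 and 24 months; intolerance at 3 months) cannot be obtained from the counts. The only supported one is 3-month vomiting, a difference of 15.3% − 4.1% = 11.2 percentage points, at the visit section 2.5 does not list for it. At the listed visits the differences are 5.8, 6.1 and 1.6 points, none below 0.05.

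This does not show that the arms are alike after 3 months. Group A has the higher proportion at every visit and events are few, so the result is no demonstrated difference, not equality. Likewise, 0 v 0 for intolerance shows only that nobody seen at 12 or 24 months was recorded as vomiting almost daily.

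The conclusion assumes that the Table 3 counts and denominators are correct, that the row p entries belong to the rows in which they appear, and that the sentence in section 2.5 means what it says. If records show that 3 months was a scheduled assessment, the timing objection falls. The 3-month result would then be a nominal finding at one of four visits, and the four unsupported entries would still be wrong.

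**What to change.** 1. Correct the P<0.05 entries for vomiting at 6, 12 and 24 months and for intolerance at 3 months. Print exact p-values and name the test.
2. Reconcile section 2.5 with Table 3. Unless 3 months can be shown to have been a scheduled assessment for these two outcomes, label the 3-month results descriptive and base the between-arm statement on 6, 12 and 24 months, where no difference is shown at 0.05.
3. State beside the aim and in the Table 3 footnote that tolerance to food is measured only as near-daily vomiting, with 2, 1, 0 and 0 events, all in Group A, and that 0 v 0 does not show equal food tolerance.
4. State whether intolerant patients are also counted in the vomiting row.

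Cost: recalculation from data already held, a check of the visit schedule, and a few sentences. The downside is that, unless the 3-month assessment is shown to have been scheduled, the claim of significantly more vomiting after the 2 cm resection is reduced to one descriptive early result.

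### The secondary endpoints are listed in three non-matching ways, and no table row reports surgical complications or deaths by arm

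*Combined protocol and SAP*

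**What the plan says.** The secondary endpoints are stated in three places.

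- **Background:** "Secondary aim-points are represented by evaluation of differences in morbidity, mortality, tolerance to food, incidence of reflux symptoms", followed by the GERD-HRQL score.
- **Section 2.2 Study Design:** "Secondary outcomes were evaluation of morbidity, mortality, incidence of reflux symptoms and Quality of Life score between the Groups". Food tolerance is absent and the quality-of-life instrument is not named.
- **Section 2.5 Post-operative evaluation:** "The secondary endpoints were GERD and esophagitis studied with Upper endoscopy and GERD score". Morbidity and mortality are absent, and esophagitis appears for the first time as an endpoint.

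Section 2.5 also describes what was assessed: "All patients were actively clinical followed up regularly at 3, 6, 12 and 24, included GERD-HRQL", and "Significant vomiting and food intolerance were evaluated at 6, 12 and 24 months follow-up". It defines significant vomiting and food intolerance, and places upper endoscopy at 12 or 24 months. It describes no assessment of surgical complications or death.

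After section 2.6, four results tables are listed and then shown filled in: demographics, weight, GERD-HRQL, and endoscopy ("Table 4: Endoscopy Preoperative and at 1 and 2 years follow-up into two Groups"). Under the exclusion criteria in section 2.2, patients converted to open surgery are excluded.

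**The concern.** All three lists are current text, and they disagree on whether morbidity and mortality are secondary outcomes at all. The results tables contain no row for death or for the surgical complications that the Background names.

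This matters because complications are part of the case for comparing the two distances. For the more distant resection, the Background cites prevention of distal stenosis and lower intraluminal pressure, "potentially leading to a lower incidence of fistula and/or reflux". Fistula is one argument among several, and the stated primary aim is excess weight loss. Even so, a reader choosing between 2 cm and 6 cm would want complications by arm next to weight and reflux.

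Three unequal lists also leave it open which secondary results count as planned.

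**Working it through.** The documents give no complication rate or count, so there is no planned figure to reproduce. The sample size of 138 does not bear on this point.

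**Step 1. Set the lists beside the assessments and the table rows.**

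| Item | Background | 2.2 | 2.5 endpoint sentence | Assessment in 2.5 | Row in Tables 1–4 |
|---|---|---|---|---|---|
| Morbidity (surgical) | yes | yes | no | none | none |
| Mortality | yes | yes | no | none | none |
| Food tolerance | yes | no | no | defined; 6, 12, 24 months | Table 3 |
| Reflux symptoms / GERD | yes | yes | yes | 3, 6, 12, 24 months, through GERD-HRQL | Table 3 |
| GERD-HRQL / quality-of-life score | yes | yes, if the unnamed score is GERD-HRQL | yes | 3, 6, 12, 24 months | Table 3 |
| Endoscopic esophagitis | no | no | yes | 12 or 24 months | Table 4 |

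Of six distinct items, the Background has 5, section 2.2 has 4 and section 2.5 has 3. Only reflux and a score are common to all three. Two items, surgical morbidity and mortality, have neither an assessment nor a row.

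**Step 2. Check the named complications.** The Background names leak, hemorrhage, splenic injury, stenosis and GERD. Of these five, only GERD has rows.

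**Step 3. Check the analysis text.** Section 2.6 names tests for baseline comparisons and for change from before to after surgery. It gives no definition, grading, time window or between-arm method for morbidity or mortality.

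**Step 4. Check denominators.** 75 + 75 = 150 patients were randomized, and 131 were followed at 24 months (65 and 66). So 150 − 131 = 19 are missing then: 10 in Group A and 9 in Group B. Using 75 and 75 for late events would count those 19 as event-free.

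**Step 5. What such a table could show.** The event counts here are assumed.

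- With 0 events in 75, the two-sided 95% upper limit is 1 − 0.025^(1/75) = 4.8%. The one-sided 95% limit is 1 − 0.05^(1/75) = 3.9%.
- Fisher's exact test, two-sided, 75 per arm: 5 vs 0 gives p = 0.058; 6 vs 0 gives p = 0.028.

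**Step 6. Whether the status of esophagitis matters.** From Table 4 at 2 years, grade B or worse is (9+1)/52 = 10/52 vs 3/53, Fisher p = 0.042. Any grade is (5+9+1)/52 = 15/52 vs (5+3)/53 = 8/53, p = 0.10. No cut-off is stated, and at 2 years the choice decides which side of 0.05 the result falls on.

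**The case against.** Several parts of the case on the other side stand.

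- The tables do not simply mirror the list in section 2.5. Table 3 has by-arm rows for vomiting and food intolerance, which are not in that section's endpoint sentence. A reader might infer that food tolerance was dropped, and the documents show otherwise.
- In a broad sense, reflux, vomiting and esophagitis are morbidity, and Tables 3 and 4 report them by arm. But the Background lists morbidity separately from food tolerance and reflux, so the gap is surgical morbidity and death.
- Esophagitis is not clearly a foreign endpoint. The pre-operative evaluation grades it within the reflux work-up, and it can be read as an objective measure of the reflux aim.
- A reader might infer that complications and deaths were not reported at all, or that endpoints were selected after the results were known. The documents support neither. The table list does not claim to be the whole report, rare events could be given in text, and Figure 1 is not shown and might record deaths or conversions. A flow diagram would still not give a comparison of morbidity by arm.
- The event counts in step 5 are hypothetical. They show low precision for rare events, not an effect of the inconsistent lists.

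**Conclusion.** The point holds in a limited form. The three lists contradict each other, and two outcomes named in both the Background and section 2.2 have no definition, no scheduled assessment and no row in the tables. Two of the five secondary aims in the Background are affected. The conversion exclusion adds to the gap, because an operative event that led to conversion could leave the data uncounted. The documents do not say whether any conversion occurred.

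The primary outcome is not touched, so this is a change that should be made rather than a fatal flaw. A morbidity table at this size would be mainly descriptive: a finding of no significant difference would be weak evidence of equal safety, which is why intervals are needed. This rests on reading morbidity as surgical morbidity and on taking 75 and 75 as all randomized patients, as section 2.2 states.

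**What to change.** 1. Use one list of secondary endpoints in the Background and sections 2.2 and 2.5. Name the quality-of-life instrument. State whether endoscopic esophagitis is a secondary endpoint or exploratory, and with which grade cut-off.
2. Define surgical morbidity and mortality, with a grading and a time window.
3. Add a table by assigned group for leak, hemorrhage, splenic injury, stenosis, re-operation, conversion and death, each with counts, a risk difference and an exact 95% confidence interval.
4. Use all 75 and 75 randomized patients as denominators for perioperative events within the stated window. For later events use the number followed, or a time-to-event method.
5. Reconcile this with the conversion exclusion in section 2.2 by counting converted patients in their assigned arm for this table.

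The cost is wording and one table, provided complications and deaths were recorded for every randomized patient. The documents do not confirm this. If they were not recorded, the report should say so and not claim to have answered the morbidity and mortality aim.

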	Group A (n=72)	Group B(n=73)	p>0.05	Group A(n=70)	Group B(n=71)	P<0.05	Group A(n=67)	Group B(n=69)	p	Group A(n=65)	Group B(n=66)	p>0.05
BMI	30.9 ± 5.32	34.7 ± 4.18	P<0.05	26.13 ± 7.32	31.06 ± 3.12	P<0.05	24.2 ± 3.4	27.5 ± 4.3	P<0.05	25.2 ± 4.4	26.2 ± 3.3	p>0.05
EBWL%	40.9 ± 8.1	31.60 ± 8.7	P<0.05	54.1 ± 11.3	48.20 ± 12.5	P<0.05	63.7 ± 14.1	59.6 ± 12.5	P<0.05	62.8 ± 13.1	61.6 ± 10.5	p>0.05

Results

Table 3 GERD Health-Related Quality-of-Life (GERD-HRQL) Score preoperative and postoperative scores

Patients	Preoperative 150/150		3 months follow-up 145/150		p >0.05	6 months follow-up 141/150		P <0.05	12 months follow-up 136/150		P <0.05	24 months follow-up 131/150		p >0.05
	Group A (n=75)	Group B (n=75)	Group A (n=72)	Group B (n=73)		Group A (n=70)	Group B (n=71)		Group A (n=67)	Group B (n=69)		Group A (n=65)	Group B (n=66)	
GERD HRQL Score<15			38(52.7%)	57(78%)	P <0.05	36(51.4%)	56(78.8%)	P <0.05	47(70.4%)	55(79.7%)	P <0.05	49(75.3%)	55(83.3%)	P <0.05
GERD HRQL Score >16<30	7(9.3%)	9(12%)	29(40%)	15(20.5%)	P <0.05	30(42.8%)	14(19.7%)	P <0.05	16(23.8%)	13(18.8%)	P >0.05	14(21.5%)	10(15.1%)	P >0.05
GERD HRQL Score >31	-	-	5(6.9%)	1(1.3%)	P <0.05	4(5.7%)	1(1.4%)	P <0.05	4(5.9%)	1(1.4%)	P <0.05	1(1.5%)	0	P <0.05
Significant Vomit	-	-	11(15,3%)	3(4.1%)	P <0.05	6(8.6%)	2(2.8%)	P <0.05	6(8.9%)	2(2.9%)	P <0.05	2(3.1%)	1(1.5%)	P <0.05
Intolerance to food	-	-	2(2.7%)	0	P <0.05	1(1.4%)	0	p >0.05	0	0	p >0.05	0	0	p >0.05

Table 4: Endoscopy Preoperative and at 1 and 2 years follow-up into two Groups

	Preoperative Patients 150		1 year follow-up Patients 108/150(72%)		2 years follow-up Patients 105/150(70%)	
	Group A 75	Group B 75	Group A 53	Group B 55	Group A 52	Group B 53
Esophagitis						
A	4(5.3%)	5(6.7%)	9(16.9%)	7(12.7%)	5(9.6%)	5(9.4%)
B	-	-	11(20.7%)	5(9%)	9(17.3%)	3(5.6%)
C	-	-	2(3.8%)	0	1(1.9%)	0
D	-	-				
Esophageal biopsy						
Metaplasia	-	-	0	0	0	0
Helicobacter Pylori	9(12%)	7(9.3%)				
Hiatal Hernia< 5 cm	1(1.3%)	2(2.7%)	-	-	-	-

Figure 1 Diagram of Patients eliability

Flow Diagram

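### Esophagitis is named as a secondary endpoint, but the plan states no between-arm comparison for it and Table 4 reports none

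*Combined protocol and SAP*

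**What the plan says.** Section 2.5 (Post-operative evaluation) names the endpoint: "The secondary endpoints were GERD and esophagitis studied with Upper endoscopy and GERD score". The Background and section 2.2 (Study Design) do not list esophagitis. Section 2.2 has: "Secondary outcomes were evaluation of morbidity, mortality, incidence of reflux symptoms and Quality of Life score between the Groups".

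Section 2.6 (Statistical Analysis) gives two statements of method. For baseline: "Baseline comparisons were performed using chi-square tests and T-tests". For follow-up: "Differences between preoperative and postoperative parameters were compared by Wilcoxon paired rank test". All tests are two-sided at 0.05, and no adjustment for multiple comparisons is mentioned.

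On who was scoped, section 2.5 says: "UE was performed in all patients at 12 or 24 months". Table 4 reports 108 of 150 patients at 1 year (53 in Group A, 55 in Group B) and 105 of 150 at 2 years (52 and 53). It gives grades by arm and has no p column, whereas Tables 2 and 3 print p flags at each visit.

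Grade B appears as a threshold twice. Section 2.2 excludes patients who have "GERD with esophagitis scored as or greater than grade B", and section 2.5 restricts esophageal biopsy to grade B or worse.

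**The concern.** A paired test of before against after asks whether patients changed, arm by arm or pooled. It does not ask whether resection at 2 cm and resection at 6 cm led to different results, which is the question the randomisation was set up to answer. Followed as written, the plan leaves the endoscopy endpoint uncompared.

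The gap in stated method covers every post-operative outcome, including %EWL, the primary one. Esophagitis is the sharpest case because Table 4 does not supply even the unexplained p flags of Tables 2 and 3.

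At stake is the endoscopic evidence on reflux, which the Background presents as one side of the trade-off in choosing the resection distance. Readers are left to judge by eye a ratio of about three based on few events. Some will over-read it and others will pass over it.

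**Working it through.** **Inputs (Table 4).** The grade D row is a dash preoperatively and blank at follow-up, and is taken as zero.

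- 12 months: Group A has grade A 9, B 11, C 2 of 53 scoped; Group B has 7, 5, 0 of 55.
- 24 months: Group A has 5, 9, 1 of 52; Group B has 5, 3, 0 of 53.

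**Reproducing the printed figures.** 108/150 = 72.0% and 105/150 = 70.0%. 11/53 = 20.8%, 2/53 = 3.8%, 5/55 = 9.1%, 9/52 = 17.3%, 1/52 = 1.9%, 3/53 = 5.7%. All agree with the table up to truncation of the last digit.

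**Grade B or worse.**

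- 12 months: (11+2)/53 = 13/53 = 24.5% against 5/55 = 9.1%. Ratio 2.7; 18 events.
- 24 months: (9+1)/52 = 10/52 = 19.2% against 3/53 = 5.7%. Ratio 3.4; 13 events.

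Table 4 shows no grade B to D at baseline, so these cases were not present at the preoperative endoscopy.

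**Interval.** With Wilson limits (l, u) for each arm and d = pA − pB, the Newcombe limits are d − √[(pA − lA)² + (uB − pB)²] and d + √[(uA − pA)² + (pB − lB)²].

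- 12 months: Wilson limits 0.1493 to 0.3757 (A) and 0.0395 to 0.1958 (B); d = 0.1544. Lower = 0.1544 − √(0.0960² + 0.1049²) = 0.012. Upper = 0.1544 + √(0.1304² + 0.0514²) = 0.295.
- 24 months: Wilson limits 0.1080 to 0.3190 (A) and 0.0194 to 0.1537 (B); d = 0.1357. Lower = 0.1357 − √(0.0843² + 0.0971²) = 0.007. Upper = 0.1357 + √(0.1267² + 0.0372²) = 0.268.

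**Tests and choice of cut.**

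| Outcome, visit | A | B | Difference, points (95% CI) | Fisher p | Yates p |
|---|---|---|---|---|---|
| Grade B or worse, 12 mo | 13/53 | 5/55 | 15.4 (1.2 to 29.5) | 0.040 | 0.058 |
| Grade B or worse, 24 mo | 10/52 | 3/53 | 13.6 (0.7 to 26.8) | 0.042 | 0.070 |
| Any grade, 12 mo | 22/53 | 12/55 | 19.7 (2.2 to 35.8) | 0.038 | 0.046 |
| Any grade, 24 mo | 15/52 | 8/53 | 13.8 (−2.2 to 29.0) | 0.10 | 0.14 |

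For grade B or worse, one event fewer in Group A gives Fisher p = 0.067 at 12 months and 0.073 at 24. One event more in Group B gives 0.079 and 0.092.

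**Unscoped patients.** At 12 months these are 75 − 53 = 22 and 75 − 55 = 20, together 42/150 = 28%. At 24 months they are 75 − 52 = 23 and 75 − 53 = 22, together 45/150 = 30%.

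- All counted as negative: 13/75 against 5/75, p = 0.076; 10/75 against 3/75, p = 0.078.
- Only Group A's counted as positive: 35/75 against 5/75, ratio 7.0; 33/75 against 3/75, ratio 11.0.
- Only Group B's counted as positive: 13/75 against 25/75, ratio 0.52; 10/75 against 25/75, ratio 0.40.

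The last two assumptions are bounds and are not meant to be plausible. They show that the direction of the difference is not guaranteed by the data held.

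**The case against.** The strongest objection is that grade B or worse is an eligibility limit and a biopsy trigger in this protocol. It is nowhere defined as an outcome, so choosing it once the table exists is post hoc. That stands, and the choice matters: any-grade esophagitis at 24 months gives p = 0.10. The answer is to report both cuts and label them. Only section 2.5 names esophagitis as an endpoint, which also stands, but that sentence is explicit.

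The evidence is fragile, as the one-event shifts show, and the two visits may include the same patients, so they are not two independent signals. This too stands, and it argues for an estimate with an interval, not for leaving the comparison out.

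Three stronger readings are tempting and should be resisted.

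- A reader might infer that Table 4 conceals the difference. It does not: every grade is printed by arm with its percentage. The difference is untested and unsummarised.
- A reader might infer that the endoscopy sentence in section 2.5 contradicts the 108 and 105 scoped. That is not established. Endoscopy in all patients at 12 or 24 months can mean at least one per patient, and the number scoped at least once is not given.
- A reader might infer that this is the only 24-month contrast separating the arms. As printed, Table 3 flags P<0.05 at 24 months for three rows. Those flags do not reproduce from its counts: score below 15, 49/65 against 55/66, Fisher p = 0.29; score above 31, 1/65 against 0/66, p = 0.50; significant vomiting, 2/65 against 1/66, p = 0.62. That is a separate query about Table 3 and does not strengthen the endoscopy result.

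**Conclusion.** The point holds as a gap in the analysis plan: a named secondary endpoint has no between-arm method, and the one post-operative test stated cannot provide it. Group A shows more grade B or worse esophagitis among those scoped at both visits, but with interval lower limits of only 1.2 and 0.7 points this is a signal to estimate and report, not a demonstrated harm.

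The figures rest on three assumptions: a blank grade D row means zero, the scoped patients in each arm are comparable, and the p-values are read without adjustment for multiplicity. The documents do not say why some patients were not scoped, so the second cannot be checked. Adding the comparison is a cheap improvement that should be made.

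**What to change.** 1. In section 2.6, state a between-arm comparison of esophagitis at 12 and 24 months: risk difference with Newcombe 95% CI and Fisher exact test, for grade B or worse and for any grade. Label it as specified after tabulation and unadjusted for multiplicity, and add the results to Table 4.
2. From patient-level data, add grade B or worse at any follow-up endoscopy, counting each patient once, with everyone scoped at least once as the denominator.
3. Report by arm how many patients were scoped at least once, so that the coverage statement in section 2.5 can be checked, and give the reasons for missing endoscopies where known.
4. Show sensitivity to unscoped patients in both directions, not only with them counted as negative.

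The first and fourth items need a few table rows from counts already printed. The second and third need some linkage of each patient's two visits; this cannot come from Table 4, but it requires no new endoscopy. The main downside is that a secondary comparison written after the counts were known carries less weight, and the label must say so.
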